3.2 Control of Type 1 Error

The Type 1 error rate will be controlled to no more than 5% for the primary analysis of the primary efficacy endpoint. The study will be considered positive if the primary analysis reaches statistical significance.

The other statistical analyses / efficacy parameters will all be tested at a nominal alpha of 5%, but no control for multiplicity of testing will be applied since those additional analyses will be performed mainly for signal detection and will be confirmed in a subsequent Phase 3 trial.

3.3 Analysis Population

The Intent-to-treat (ITT) Population will include all patients randomized to a treatment group who complete the baseline evaluations, regardless of having received any study treatment or not. The ITT population will be used for the primary analyses of all study endpoints, taking into consideration the specific populations described below. The patients will be kept in their randomized treatment arm for the analyses.

The Per Protocol (PP) Population will include all patients randomized to a treatment group to whom at least 5 cycles of study treatment are administered in accordance with the protocol, defined as at least 80% compliance. The PP population will serve as the basis for secondary analyses of

all study endpoints, taking into consideration the specific populations described below. The patients will be kept in the treatment arm that they actually received for the analyses.

The FEV₁ Population is a subset of the PP population and will include all patients who have validated FEV₁ values (values judged to be obtained from adequate expiratory curves by central review) for at least 4 time points of the study comprising at the minimum the baseline and Day 161 assessments. This population will be used for the secondary analyses of all FEV₁-related endpoints. The patients will be kept in the treatment arm that they actually received for the analyses.

The Protocol-Defined PEx Subset Population will include all patients who experience a protocol - defined PEx episode (\geq 4/12 Fuch symptoms and use of IV antibiotic) during the study after completing at least one cycle of study drug treatment. The patients will be kept in the treatment arm that they actually received for the analyses.

The Overall PEx Subset Population will include all patients who experience an oral or IV antibiotic treated PEx episode during the study after completing at least one cycle of study drug treatment. The patients will be kept in the treatment arm that they actually received for the analyses.

The Safety Population will include all patients randomized to a treatment group who received at least one dose of study drug treatment. This population will serve as the basis for analyses of all safety endpoints. The patients will be kept in the treatment arm that they actually received for the analyses.

The Pharmacokinetic (PK) Population will include all patients randomized to the LAU-7b treatment group and provided the C_{min} blood samples. This population will serve as the basis for the between-group comparison of the steady-state fenretinide pharmacokinetics grouped according to the *a priori* stratification factors and to compare the results with those obtained during the prior Phase Ib study.

The Healthy Control Population will consist of 20 healthy controls. The data for these patients will be collected by Laurent Pharma, and provided to JSS Medical Research for assessment of

demographic and pharmacodynamic parameters (AA, DHA), the latter for use in the Pharmacodynamic analyses.

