5.4.5 Specific Rationales for this Phase II study

5.4.5.1 Design/Structure

This is a randomized, double-blind (patients, Investigators and blinded study staff), placebo controlled, Phase II study (details are presented in Section 7.2). There will be no active control treatment but patients will undergo the Standard of Care at their institution. A randomized, double-blind study design will avoid observer bias and reduce symptoms or outcomes arising from the patients' knowledge of treatment. A parallel design will better detect treatment effects and is appropriate for this phase of development.

A Phase Ib study with fenretinide was conducted recently in adult CF patients. The safety results show that LAU-7b is well tolerated over 3 x 21-days cycles of progressively increasing oral doses up to 300 mg/day. The anticipated duration of treatment in the Phase II study is 6 cycles of 21 days, totalling around 24 weeks. Compared to the Phase Ib study, this duration of treatment will permit all safety and efficacy variables to be measured for an additional 3 months to obtain a more robust assessment that is less affected by short-term variability and influence of PEx.

The 24-weeks duration is anticipated to facilitate detection of significant changes in the primary efficacy endpoint FEV₁, and to also help determine the impact of fenretinide on secondary efficacy variables such as the PEx-related variables, weight and BMI, bone density, systemic bone formation/resorption markers as well as the Quality of Life assessments. While it is anticipated that the effect on the lipidomic and inflammation biomarkers endpoints will appear rapidly after the start of treatment, a 24-weeks duration will allow for an assessment of the durability of response for all parameters. The follow-up period of approximately one month after the last dose is deemed adequate for assessing safety, biomarkers and efficacy, because fenretinide and its metabolites are expected to reach undetectable levels within 7-10 days after the last dose. Thus, the follow-up period will be mostly on a drug free background. This period will also enable assessment of whether some effects on pharmacodynamic markers last longer than the drug systemic presence. The study also aims at gathering efficacy and additional safety information about LAU-7b in CF patients.

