12 STATISTICAL ANALYSIS

A statistical analysis plan (SAP) will provide details of the methods of analysis to address all study objectives. The SAP may be amended during the course of the study, but will be finalized before the cutoff date for any analysis.

Data summaries by treatment group will be presented. For continuous variables, data will be summarized with the number of patients, mean, standard deviation, median, and minimum and maximum values by treatment group. For categorical variables, data will be tabulated in frequency tables to display the number and proportion of patients for each category by treatment group. Baseline assessments for each outcome variable will be defined as the last measurement obtained before the first dose of study drug except the baseline FEV₁ which will be the average of the screening and baseline best values, to reduce variability. Statistical significance will be set at the 5% level.

Diligent efforts will be made to prevent missing data in the study. For example, patients who discontinue the study treatment early or initiate medication changes (including those prohibited by the protocol) should still be followed for all regularly scheduled visits for safety and relevant efficacy assessments, or for a minimum of a 1-month follow-up. A clear distinction should be made between treatment discontinuation and study withdrawal. Efficacy assessments occurring after treatment discontinuation should not be included in the per-protocol analysis.

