12.2 Analysis Populations

- **The intent-to-treat (ITT) population** will include all patients randomized to a treatment group who complete the baseline evaluations. The ITT population will be used for the primary analyses of all study endpoints, taking into consideration the specific populations described below.
- **The per-protocol (PP) population** will include all patients randomized to a treatment group to whom at least 5 cycles of study treatment are administered in accordance with the protocol. The PP population will serve as the basis for secondary analyses of all study endpoints, taking into consideration the specific populations described below.
- **The FEV₁ population** will include all patients who have validated FEV₁ values (values judged to be obtained from adequate expiratory curves by central review) for at least 4 time points of the study comprising at the minimum the baseline and Day 161 assessments.

- **The PEx subset population** will include all patients who experience an IV antibiotic treated PEx episode during the study after completing at least one cycle of study drug treatment.
- **The safety population** will include all patients randomized to a treatment group who received at least one dose of study drug treatment. This population will serve as the basis for analyses of all safety endpoints.
- **The pharmacokinetic population** will include all patients randomized to the LAU-7b treatment group and provided the C_{\min} blood samples. This population will serve as the basis for the between-group comparison of the steady-state fenretinide pharmacokinetics grouped according to the *a priori* stratification factors and to compare the results with those obtained during the prior Phase Ib study.

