12.3 Baseline and Demographic Characteristics

Demographic and baseline data will be summarized by treatment group using descriptive statistics. Demographics will include, among others, date of birth, gender, ethnicity, weight, height, body mass index. Childbearing status and pregnancy test results will be summarized descriptively for each treatment group. Protocol deviations/violations will be provided as a patient data listing only. Major protocol deviations/violations will be identified for analysis purposes.

The demographics and baseline characteristics summary will be presented for the ITT and the PP populations to allow review of the characteristics of those included in the efficacy analyses, which will be based on these analysis sets. The PEx subset will also be summarized separately.

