3.6 Subject Demographics and Baseline Characteristics

Demographic and baseline data will be summarized by treatment group using descriptive statistics. Demographics will include, among others, age, gender, race, ethnicity, weight, height, body mass index. Childbearing status and pregnancy test results will be summarized descriptively for each treatment group. Protocol deviations/violations will be provided as a patient data listing only.

The demographics and baseline characteristics summary will be presented for the ITT, PP, Protocol-Defined PEx and Overall PEx Populations.

In addition, baseline demographic data (age, gender, race, ethnicity), will be summarized in a separate table for the Healthy Control Population.

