3.14 Analysis of the Primary Efficacy Endpoints

The study will be considered successful if a statistically significant advantage for fenretinide over placebo is obtained for the absolute change in FEV₁ percent predicted from baseline to Week 24, as assessed in the ITT population. Confirmatory analyses will be conducted in the PP Population, Protocol-defined PEx Population and Overall PEx Population.

Values for percent predicted FEV₁ as well as their change relative to baseline will be tabulated by time point and descriptive statistics will be used. In the analysis of the primary efficacy endpoint, the absolute change from Baseline in FEV₁ percent predicted, including all measurements up to Week 28 (both during and after treatment measurements, including after treatment discontinuation) will be analyzed based on a mixed model for repeated measures, with the following specifications:

- The dependent variables will be all the absolute changes in FEV₁ percent predicted from Baseline to each time point, including Week 28;
- The fixed effects will be the treatment group, the visit and the treatment-by-visit interaction;
- The random effect will be the patient;
- An unstructured variance-covariance structure will be adopted as the default structure; alternate variance-covariance structures may be adopted as appropriate.
- The model will be adjusted for the following *à priori* stratification categories:
 - FEV₁ percent predicted determined at Baseline (<70% versus ≥70% predicted),
 - PEx frequency in the prior year (≤3 versus > 3 PEx episodes),
 - Co-administration or not of Kalydeco® (ivacaftor), Orkambi® (ivacaftor/lumacaftor), Symdeko® (ivacaftor/tezacaftor) or another commercially available CFTR modulator product (yes versus no);

- The difference between treatment means at each time point and its 95% confidence interval will be estimated.
- Stratum-specific estimates based on Least Square Means will be generated

The primary result obtained from the model will be the treatment effect at Week 24. The estimated mean treatment effect, a 95% confidence interval, and a 2-sided p-value will be generated.

The analysis will be repeated with the addition of the following covariates in the model:

- Baseline use of Trikafta (yes versus no);
- Effect of the pandemic confinement (pre versus post pandemic onset) (described in Section 3.14.1)

Alternative methods will be used if necessary due to data not meeting the standard requirements for the proposed analysis.

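### The SAP does not carry forward the protocol's rule that keeps FEV1 values taken after stopping study drug out of the per-protocol analysis

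*SAP*

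**What the plan says.** **Who is in PP.** Protocol 12.2 takes randomized patients "to whom at least 5 cycles of study treatment are administered in accordance with the protocol". SAP 3.3 keeps the five-cycle threshold and adds a meaning for the last phrase: "at least 5 cycles of study treatment are administered in accordance with the protocol, defined as at least 80% compliance". The SAP's FEV1 population is a subset of PP. It needs validated values at four or more time points, including baseline and Day 161, and sets no on-drug condition.

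**Which values count.** Protocol section 12 sets a data rule: "Efficacy assessments occurring after treatment discontinuation should not be included in the per-protocol analysis". The SAP contains no equivalent sentence. SAP 3.14 gives one model for the primary endpoint, covering measurements to Week 28, "both during and after treatment measurements, including after treatment discontinuation". On the other populations it says: "Confirmatory analyses will be conducted in the PP Population, Protocol-defined PEx Population and Overall PEx Population".

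**Deviations.** Protocol 12.3 has two consecutive sentences. One limits the reporting of deviations to a listing. The next reads "Major protocol deviations/violations will be identified for analysis purposes". SAP 3.6 repeats the first ("Protocol deviations/violations will be provided as a patient data listing only") and omits the second.

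**Record of changes.** The table in SAP section 5 mentions neither omission.

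**The concern.** The PP run is the adherence-based check on the primary result. The protocol intended it to use efficacy values only while patients were on their assigned regimen. A programmer working from the SAP alone would fit the SAP 3.14 model to PP patients and keep values taken after study drug had been stopped, including at the primary time point. Agreement between ITT and PP would then say less about patients treated as planned than the protocol meant it to.

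The omitted sentence on major deviations is a smaller matter of the same kind. Without it, the SAP contains no step at which such deviations are flagged before the PP analysis is run.

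**Working it through.** **1. Reproduce the schedule.** Inputs: six 28-day cycles, 21 days on and 7 off (Protocol 9.5), starting on Day 1. Cycle c is dosed from Day 28(c-1)+1 to Day 28(c-1)+21.

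| Cycle | Dosing days | Days off drug at Day 161 if this is the last cycle |
|---|---|---|
| 4 | 85-105 | 56 |
| 5 | 113-133 | 28 |
| 6 | 141-161 | 0 |

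The sixth cycle ends on Day 161, which matches the End-of-Cycle 6 visit in the schedule of events.

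**2. Does a patient who stops after Cycle 5 enter PP?** SAP 3.5 ends exposure at the last dose. SAP 3.12 computes compliance as 100 x (1 - interruption days / (exposure - planned drug-free days)).

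- Exposure: 133 - 1 + 1 = 133 days.
- Planned drug-free days between Cycles 1 and 5: 4 x 7 = 28.
- Denominator: 133 - 28 = 105.
- Compliance with no interruption: 100 x (1 - 0/105) = 100%.

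The patient therefore meets both parts of the SAP rule. Even if the 21 dosing days of Cycle 6 were counted as interruption over the same denominator, the result is 100 x (1 - 21/105) = 80%, which still meets the floor.

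**3. Can the off-drug value exist?** Yes. Protocol 8.4 and section 12 allow or encourage patients who stop treatment to keep to the planned visits.

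**4. How far off drug?**

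- Stop after Cycle 5: 161 - 133 = 28 days, or 28-30 with the Day 161-163 window in Protocol 9.2.5.
- Stop during Cycle 6 (last dose Day 141 to 160): 1-20 days.

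Protocol 5.4.5.1 gives the comparison: "fenretinide and its metabolites are expected to reach undetectable levels within 7-10 days after the last dose".

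**5. Is the value removed anywhere else?** No. The Week 24 sensitivity analysis in SAP 3.14.2 drops later data but keeps Day 161. The FEV1 population requires a Day 161 value without asking whether the patient was on drug.

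**6. Illustrative size.** Dilution = share affected x fraction of effect lost x 4 points (the design difference in SAP 2.6). The shares and fractions are assumptions.

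| Share of PP active patients off drug at Day 161 | All of effect lost | Half of effect lost |
|---|---|---|
| 5% | 0.2 | 0.1 |
| 10% | 0.4 | 0.2 |
| 15% | 0.6 | 0.3 |

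**The case against.** **The SAP never says in words that the PP run keeps these values.** This is correct. The parenthetical describes the primary analysis, which is assessed in ITT. The same wording stands in Protocol 12.4.1 alongside the exclusion in section 12, and the SAP introduction says that it follows the protocol. The protocol rule might therefore be meant to apply silently. What stands is that inclusion is inferred from a single model specification without a PP exception. But the protocol holds both sentences and the SAP holds only the one that includes the values, so the text needs correcting on either reading.

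**The 28-day case is one scenario.** This also stands. A reader might infer that every five-cycle patient is 28 days off drug at Day 161. That is not so: a patient may have missed an earlier cycle and be on drug at that visit. The five-cycle threshold is also the protocol's own. The fault lies in the missing data rule.

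**The size is loosely anchored.** The only attrition figure is dropout of at most 10% from all causes (SAP 2.6). It does not measure stopping drug while staying in follow-up, and it lends no support to 15%. Drug washout is not evidence of how fast FEV1 changes, so complete loss of effect is an upper bound.

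**On deviations, a reader might infer more than the documents support.** One could conclude that the SAP downgraded deviations to a listing, or that it retains patients whom the protocol would remove from PP. Neither holds. The listing sentence is in Protocol 12.3 itself, and no passage excludes major deviators from PP. Patients who took the wrong study drug need no new exclusion, because SAP 3.3 already analyses PP patients by treatment received.

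**Conclusion.** The point holds as an unrecorded gap between the two documents. Protocol section 12 bars post-discontinuation efficacy values from PP. The SAP omits the bar and, read as written, lets them in.

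The schedule and compliance arithmetic rest only on figures in the documents. The 28-day gap applies to a permanent stop after Cycle 5 with continued visits, and the 1-20 day gap to a stop during Cycle 6. The number of such patients is not given. The 0.2-0.6 point dilution assumes 5-15% affected and total loss of a 4-point effect; with half the effect lost it is 0.1-0.3 points.

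A reader might infer that the trial's conclusion is at risk. It is not: SAP 3.14 rests success on ITT, where post-discontinuation values are included by design. The consequence is confined to a named confirmatory analysis and to the FEV1 population nested within it. The missing sentence on major deviations is a secondary omission.

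**What to change.** 1. In SAP 3.3 and 3.14, state that the PP and FEV1-population analyses exclude FEV1 values taken after permanent discontinuation of study drug before the planned end of Cycle 6. Word it so that completers' scheduled Day 189 values are kept.
2. State that an excluded Day 161 value does not satisfy the Day 161 requirement of the FEV1 population.
3. If the sponsor prefers to keep these values in PP, record and justify the departure from Protocol section 12 in SAP section 5.
4. In SAP 3.6, restore the protocol's sentence on identifying major deviations, and do this at a blinded review before database lock. Any rule that then removes such patients from PP would be a new proposal, to be labelled as such in section 5.

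Leave the ITT analysis unchanged. The cost is a few sentences, one blinded review and somewhat fewer Week 24 values in PP. The excluded patients' earlier on-drug values would still contribute to the repeated-measures model in PP.

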3.4 Subject Disposition and Discontinuations

Patient disposition will be summarized for the total enrolled population and by treatment group.

The following data will be presented:

- The number of patients who were screened, enrolled and randomized
- The number and proportion of patients in each analysis population
- The number and percentage of patients who completed the study
- The number and percentage of patients who discontinued prematurely from the study and the associated reasons.
- The number and percentage of patients who attended each follow-up visit.

3.5 Treatment Exposure and Dosing

The duration of study drug exposure is defined as follows: last dose date minus first dose date plus 1 day, regardless of any interruptions in dosing. If the last dose date of study drug is missing, the patient's discontinuation or completion date will be used for analysis purpose. Duration of study drug exposure will be summarized descriptively as a continuous variable (number, mean, SD, median, minimum, and maximum), by treatment group, using the Safety population.

3.6 Subject Demographics and Baseline Characteristics

Demographic and baseline data will be summarized by treatment group using descriptive statistics. Demographics will include, among others, age, gender, race, ethnicity, weight, height, body mass index. Childbearing status and pregnancy test results will be summarized descriptively for each treatment group. Protocol deviations/violations will be provided as a patient data listing only.

The demographics and baseline characteristics summary will be presented for the ITT, PP, Protocol-Defined PEx and Overall PEx Populations.

In addition, baseline demographic data (age, gender, race, ethnicity), will be summarized in a separate table for the Healthy Control Population.

3.7 Medical History

Medical conditions will be coded using the Medical Dictionary for Regulatory Activities (MedDRA) and the number and percentage of subjects with medical history will be reported by System Organ Class (SOC) and Preferred Term (PT).

3.8 Vital Signs/Physical Examination/ECG

Vital signs (blood pressure, temperature, heart rate, oxygen saturation and respiration rate) will be presented at each time point using descriptive statistics (mean, standard deviation, median, minimum, and maximum). Change from baseline values for each variable will also be presented by treatment group.

The number and percentage of patients that meet the abnormal criteria over time during the TEAE period will be presented by treatment group. The specific changes of interest are:

- Diastolic Blood Pressure ≤ 45 mmHg and decrease from baseline ≥ 10 mmHg, Diastolic Blood Pressure ≥ 110 mmHg and increase from baseline ≥ 10 mmHg;
- Systolic Blood Pressure ≥ 160 mmHg and increase from baseline ≥ 20 mmHg
- Temperature $\leq 35^{\circ}\text{C}$ and $\geq 38^{\circ}\text{C}$;
- Heart rate ≤ 50 bpm and decrease from baseline ≥ 20 bpm, heart rate ≥ 120 bpm and increase from baseline ≥ 20 bpm;
- Oxygen saturation values and respiratory rate determined by the Investigator to be clinically abnormal.

The number and percentage of subjects reporting normal and abnormal (NCS and CS) for physical exam at each visit will be described by treatment group.

For ECG measurements, a summary of raw values and change from screening values will be provided by treatment group for each scheduled time point for the following standard digital ECG

measurements: PR, QT, and QT corrected for heart rate (QTc) intervals, QRS duration, and HR. The number and percentage of patients with shift changes from screening (normal/missing, not clinically significant, and clinically significant according to overall ECG evaluation) to the worst ECG evaluation during the TEAE period will be tabulated by treatment group.

In addition, the number and percentage of patients will be tabulated by maximum on-treatment value of QT/QTc intervals, categorized as ≤ 500 msec and > 500 msec, as well as maximum on-treatment change from baseline value of QT/QTc intervals, categorized as > 30 msec.

No statistical analyses of vital signs or ECG data are planned.

